7.2.2 Reporting of Pregnancy and Lactation to the Sponsor and to Merck

Although pregnancy and lactation are not considered adverse events, it is the responsibility of investigators or their designees to report any pregnancy or lactation in a subject (spontaneously reported to them) that occurs during the trial.

Pregnancies and lactations that occur after the consent form is signed but before treatment allocation/randomization must be reported by the investigator if they cause the subject to be excluded from the trial, or are the result of a protocol-specified intervention, including but not limited to washout or discontinuation of usual therapy, diet, placebo treatment or a procedure.

Pregnancies and lactations that occur from the time of treatment allocation/randomization through 120 days following cessation of Sponsor's product, or 30 days following cessation of treatment if the subject initiates new anticancer therapy, whichever is earlier, must be reported by the investigator. All reported pregnancies must be followed to the completion/termination of the pregnancy. Pregnancy outcomes of spontaneous abortion, missed abortion, benign hydatidiform mole, blighted ovum, fetal death, intrauterine death, miscarriage and stillbirth must be reported as serious events (Important Medical Events). If the pregnancy continues to term, the outcome (health of infant) must also be reported.

Such events must be reported within 24 hours to the Sponsor and within 2 working days to Merck Global Safety. (Attn: Worldwide Product Safety; [contact])

7.2.3 Immediate Reporting of Adverse Events to the Sponsor and to Merck

7.2.3.1 Serious Adverse Events

A serious adverse event is any adverse event occurring at any dose or during any use of study treatment that:

- Results in death;
- Is life threatening;
- Results in persistent or significant disability/incapacity;
- Results in or prolongs an existing inpatient hospitalization;
- Is a congenital anomaly/birth defect;
- Is another important medical event
- Note: In addition to the above criteria, adverse events meeting either of the below criteria, although not serious per ICH definition, are reportable to the Merck in the same timeframe as SAEs to meet certain local requirements. Therefore, these events are considered serious by Merck for collection purposes.
 - Is a new cancer (that is not a condition of the study);
 - Is associated with an overdose.

Refer to Table 7 for additional details regarding each of the above criteria.

Progression of the cancer under study is not considered an adverse event unless it results in hospitalization or death.

Any serious adverse event, or follow up to a serious adverse event, including death due to any cause other than progression of the cancer under study that occurs to any subject from the time of starting study treatment through 90 days following cessation of treatment, or the initiation of new anti-cancer therapy, whichever is earlier, whether or not related to study treatment, must be reported **within 24 hours** to the Sponsor (Moffitt Cancer Center) and **within 2 working days** to Merck Global Safety.

Additionally, any serious adverse event, considered by an investigator who is a qualified physician to be related to Merck product that is brought to the attention of the investigator at any time following consent through the end of the specified safety follow-up period specified in the paragraph above, or at any time outside of the time period specified in the previous paragraph also must be reported immediately to the Sponsor and to Merck Global Safety.

All subjects with serious adverse events must be followed up for outcome.

SAE reports and any other relevant safety information are to be forwarded to the Merck Global Safety [contact]

A copy of all 15 Day Reports and Annual Progress Reports is submitted as required by FDA, European Union (EU), Pharmaceutical and Medical Devices agency (PMDA) or other local regulators. Investigators will cross reference this submission according to local regulations to the Merck Investigational Compound Number (IND, CSA, etc.) at the time of submission. Additionally investigators will submit a copy of these reports to Merck & Co., Inc. (Attn: Worldwide Product Safety; [contact]) at the time of submission to FDA.

7.2.3.2 Events of Clinical Interest

Selected non-serious and serious adverse events are also known as Events of Clinical Interest (ECI) and must be reported within 24 hours to the Sponsor and within 2 working days to Merck Global Safety. (Attn: Worldwide Product Safety; [contact]).

For the time period beginning when the first dose of study treatment is administered, any ECI, or follow up to an ECI, that occurs to any subject must be reported within 24 hours to the Sponsor and within 2 working days to Merck Global Safety if it is the result of a protocol-specified intervention, including but not limited to washout or discontinuation of usual therapy, diet, placebo treatment or a procedure.

For the time period beginning at first study treatment through 90 days following cessation of treatment, or 30 days following cessation of treatment if the subject initiates new anticancer therapy, whichever is earlier, any ECI, or follow up to an ECI, whether or not related to Merck product, must be reported within 24 hours to the Sponsor and within 24 hours to Merck Global Safety.

Events of clinical interest for this trial include:

- 1. an overdose of Merck product, as defined in Section 7.2.1 Definition of an Overdose for This Protocol and Reporting of Overdose to the Sponsor, that is not associated with clinical symptoms or abnormal laboratory results.
- 2. an elevated AST or ALT lab value that is greater than or equal to 3X the upper limit of normal and an elevated total bilirubin lab value that is greater than or equal to 2X the upper limit of normal and, at the same time, an alkaline phosphatase lab value that is less than 2X the upper limit of normal, as determined by way of protocol-specified laboratory testing or unscheduled laboratory testing.*

*Note: These criteria are based upon available regulatory guidance documents. The purpose of the criteria is to specify a threshold of abnormal hepatic tests that may require an additional evaluation for an underlying etiology.

7.2.4 Evaluating Adverse Events

An investigator who is a qualified physician will evaluate all adverse events according to the NCI Common Terminology for Adverse Events (CTCAE), version 4.0. Any adverse event which changes CTCAE grade over the course of a given episode will have each change of grade recorded on the adverse event case report forms/worksheets.

All adverse events regardless of CTCAE grade must also be evaluated for seriousness.

Table 7 Evaluating Adverse Events

An investigator who is a qualified physician, will evaluate all adverse events as to:

V4.0 CTCAE Grading	Grade 1	Mild; asymptomatic or mid symptoms; clinical or diagnostic observations only; intervention not indicated.							
	Grade 2	Moderate; minimal, local or noninvasive intervention indicated; limiting age-appropriate instrumental ADL.							
	Grade 3	Severe or medically significant but not immediately life-threatening; hospitalization or prolongation or hospitalization indicated; disabling; limiting self-care ADL.							
	Grade 4	Life threatening consequences; urgent intervention indicated.							
	Grade 5	Death related to AE							
Seriousness	ss A serious adverse event is any adverse event occurring at any dose or during any use of Merck product that:								
	†Results in d	leath; or							
		tening; or places the subject, in the view of the investigator, at immediate risk of death from the event as it occurred (Note: This does not include an that, had it occurred in a more severe form, might have caused death.); or							
	†Results in a	persistent or significant disability/incapacity (substantial disruption of one's ability to conduct normal life functions); or							
	hospitalizatio worsened is r	or prolongs an existing inpatient hospitalization (hospitalization is defined as an inpatient admission, regardless of length of stay, even if the n is a precautionary measure for continued observation. (Note: Hospitalization for an elective procedure to treat a pre-existing condition that has not not a serious adverse event. A pre-existing condition is a clinical condition that is diagnosed prior to the use of a Merck product and is documented in medical history.); or							
	†Is a congenital anomaly/birth defect (in offspring of subject taking the product regardless of time to diagnosis);or								
		teer (that is not a condition of the study) (although not serious per ICH definition, is reportable to the Sponsor within 24 hours and to Merck within 2 s to meet certain local requirements); or							
	Is an overdose (whether accidental or intentional). Any adverse event associated with an overdose is considered a serious adverse event for collection purposes. An overdose that is not associated with an adverse event is considered a non-serious event of clinical interest and must be reported within 24 hours to the Sponsor and to Merck within 2 working days								

	based upon appr	her important medical events that may not result in death, not be life threatening, or not require hospitalization may be considered a serious adverse event when, ed upon appropriate medical judgment, the event may jeopardize the subject and may require medical or surgical intervention to prevent one of the outcomes ed previously (designated above by a †).								
Duration	Record the start	and stop dates of the adverse event. If less than 1 day, indicate the appropriate length of time and units								
Action taken	Did the adverse	d the adverse event cause Merck product to be discontinued?								
Relationship to Merck Product	who is a qualifie that a medically intended as refer available inform. The following of their respective of	omponents are to be used to assess the relationship between Merck product and the AE; the greater the correlation with the components and elements (in number and/or intensity), the more likely Merck product caused the adverse event (AE):								
	Exposure	Is there evidence that the subject was actually exposed to Merck product such as: reliable history, acceptable compliance assessment (pill count, diary, etc.), expected pharmacologic effect, or measurement of drug/metabolite in bodily specimen?								
	Time Course	Did the AE follow in a reasonable temporal sequence from administration of Merck product? Is the time of onset of the AE compatible with a drug-induced effect (applies to trials with investigational medicinal product)?								
	Likely Cause	Is the AE not reasonably explained by another etiology such as underlying disease, other drug(s)/vaccine(s), or other host or environmental factors								

Relationship	The following of	components are to be used to assess the relationship between the test drug and the AE: (continued)
to Merck	Dechallenge	Was Merck product discontinued or dose/exposure/frequency reduced?
Product		If yes, did the AE resolve or improve?
(continued)		If yes, this is a positive dechallenge. If no, this is a negative dechallenge.
		(Note: This criterion is not applicable if: (1) the AE resulted in death or permanent disability; (2) the AE resolved/improved despite continuation of the Sponsor's product; or (3) the trial is a single-dose drug trial); or (4) Sponsor's product(s) is/are only used one time.)
	Rechallenge	Was the subject re-exposed to Merck product in this study?
		If yes, did the AE recur or worsen?
		If yes, this is a positive rechallenge. If no, this is a negative rechallenge.
		(Note: This criterion is not applicable if: (1) the initial AE resulted in death or permanent disability, or (2) the trial is a single-dose drug trial); or (3) Sponsor's product(s) is/are used only one time).
		NOTE: IF A RECHALLENGE IS PLANNED FOR AN ADVERSE EVENT WHICH WAS SERIOUS AND WHICH MAY HAVE BEEN CAUSED BY MERCK PRODUCT, OR IF REEXPOSURE TO MERCK PRODUCT POSES ADDITIONAL POTENTIAL SIGNIFICANT RISK TO THE SUBJECT, THEN THE RECHALLENGE MUST BE APPROVED IN ADVANCE BY THE SPONSOR AS PER DOSE MODIFICATION GUIDELINES IN THE PROTOCOL.
	Consistency with Trial Treatment Profile	Is the clinical/pathological presentation of the AE consistent with previous knowledge regarding Merck product or drug class pharmacology or toxicology?
	of relationship will the above elements	be reported on the case report forms /worksheets by an investigator who is a qualified physician according to his/her best clinical judgment, including .
Record one of the	he following	Use the following scale of criteria as guidance (not all criteria must be present to be indicative of Merck product relationship).
Yes, there is a repossibility of Morelationship.		There is evidence of exposure to Merck product. The temporal sequence of the AE onset relative to the administration of Merck product is reasonable. The AE is more likely explained by Merck product than by another cause.
No, there is not possibility of Mo		Subject did not receive the Merck product OR temporal sequence of the AE onset relative to administration of Merck product is not reasonable OR the AE is more likely explained by another cause than the Merck product. (Also entered for a subject with overdose without an associated

relationship	AE.)
-	

7.2.5 Sponsor Responsibility for Reporting Adverse Events

All Adverse Events will be reported to regulatory authorities, IRB/IECs and investigators in accordance with all applicable global laws and regulations.

8.0 STATISTICAL ANALYSIS PLAN

8.1 Statistical Analysis Plan Summary

The number of patients for the dose escalation cohort will depend on the safety of dose level 1. There are two dose escalation levels and therefore the maximum sample size for the dose escalation cohorts will be 12 patients. In the dose expansion cohort, a total of 20 evaluable patients will be enrolled to confirm the safety at this dose and assess response to treatment. Therefore, the maximum sample size of the study is 32 patients. The sample size of 26 patients in treated at the MTD dose (20+3 patients from dose expansion cohort and 6+/-3 patients from the dose escalation) will give a two-sided 95% confidence interval (95%CI) of 39% to 79% for a 12-month overall survival rate of 60% when there is no censored data. If the 12-months overall survival rate increases to 80%, the corresponding 95%CI will be 60% to 93%. A two-sided 95% confidence interval for the median overall survival time is from 10 months to 23 months when the estimate of median overall survival time is 14.6 months and the percent censoring is anticipated to be 10%. These results assume Type-II Censoring and an exponential distribution of overall survival times with mean survival time of 21 months.

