1.0 TRIAL SUMMARY

Abbreviated Title	Phase I trial of pembrolizumab with vorinostat and temozolomide for newly diagnosed glioblastoma
Trial Phase	Ib
Clinical Indication	Newly diagnosed glioblastoma
Trial Type	Open label
Type of control	Not applicable
Route of administration	Intravenous, Oral
Trial Blinding	Not applicable
Treatment Groups	1 Group
Number of trial subjects	32
Estimated enrollment period	24 months
Estimated duration of trial	36 months
Duration of Participation	24 months
Estimated average length of treatment per patient	15 months

[figure not shown]

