2.0 TRIAL DESIGN

2.1 Trial Design

This is a standard 3+3 design and will include 2 cohorts: 1) dose escalation cohort, and 2) dose expansion cohort. Dose escalation will occur separately for concurrent radiotherapy part of treatment and maintenance part of treatment.

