2.2 Trial Diagram

Dose Escalation Phase

Dose Escalation Schedule During Radiotherapy Phase					
Dose Level	Dose				
	Pembrolizumab Vorinostat				
Level -1	200 mg IV every 3 weeks	100 mg/day orally on days 1-5 every week during radiotherapy			
Level 1	200 mg IV every 3 weeks	200 mg/day orally on days 1-5 every week during radiotherapy			
Level 2	200 mg IV every 3 weeks	300 mg/day orally on days 1-5 every week during radiotherapy			
	Dose Escalation S	Schedule During Maintenance Phase			
Dose Level Dose					
	Pembrolizumab	Vorinostat			
Level -1	200 mg IV every 3 weeks	200 mg/day orally 1 week on 1 week off after radiotherapy			
Level 1	200 mg IV every 3 weeks	300 mg/day orally 1 week on 1 week off after radiotherapy			
Level 2	200 mg IV every 3 weeks	400 mg/day orally 1 week on 1 week off after radiotherapy			

Twenty patients will be treated with vorinostat at MTD (from dose escalation phase), pembrolizumab, temozolomide and radiation

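### Section 8.1's maxima of 12 escalation patients and 32 in total hold only for two-level paths, and its 20+3 for the expansion disagrees with the stated 20

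*Combined protocol and SAP*

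**What the plan says.** Section 2.1 sets up a 3+3 design with an escalation and an expansion cohort, and adds: "Dose escalation will occur separately for concurrent radiotherapy part of treatment and maintenance part of treatment". Sections 2.2 and 5.3 list Levels -1, 1 and 2 for each phase, with Level 1 as the start.

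Section 8.1 begins with "The number of patients for the dose escalation cohort will depend on the safety of dose level 1". It continues with "There are two dose escalation levels and therefore the maximum sample size for the dose escalation cohorts will be 12 patients", then "In the dose expansion cohort, a total of 20 evaluable patients will be enrolled", and concludes "Therefore, the maximum sample size of the study is 32 patients". Section 1.0 gives 32 under "Number of trial subjects".

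For the precision statement, Section 8.1 describes 26 patients at the MTD as "20+3 patients from dose expansion cohort and 6+/-3 patients from the dose escalation". Section 2.2 gives the expansion as: "Twenty patients will be treated with vorinostat at MTD (from dose escalation phase), pembrolizumab, temozolomide and radiation".

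Section 5.3 reports that vorinostat during radiotherapy was lowered to Level -1 because of DLT and that this dose is being expanded. It puts the maintenance escalation to Level 2 in the present tense, which may be a status report or a description of the plan.

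**The concern.** A stated maximum should cover every path that the decision rules allow. Section 8.1 derives 12 from two levels, but each ladder has three and the third is not hypothetical. If all three are used, a reader cannot tell whether enrollment would pass 32, or whether 32 would be held and fewer than 26 patients treated at the maintenance MTD. No section states how a patient is counted across the two ladders.

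The expansion count also differs within one paragraph of Section 8.1. The paragraph uses 20 to reach 32, then 20+3 in the make-up of the 26.

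At stake are the approved enrollment figure and the supply planned for it. No hypothesis test is involved: the trial has one arm, and survival is a secondary, descriptive outcome.

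**Working it through.** **Inputs.** Two levels, 20 in expansion, and maxima of 12 and 32 (Section 8.1). Three levels per ladder (Sections 2.2 and 5.3). Cohorts of three and the decision table (Section 5.3.1). MTD with toxicity in no more than one of six (Section 5.3). The documents give no DLT rates, so those below are assumptions.

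**1. The plan's own figures.** 2 × 6 = 12 and 12 + 20 = 32; both reproduce. The intervals reproduce at n = 26:
- Exact binomial, with x = 26p and limits at the 2.5% point of Beta(x, n−x+1) and the 97.5% point of Beta(x+1, n−x): 39.1% to 78.5% at 60% (printed 39 to 79), and 59.8% to 93.0% at 80% (printed 60 to 93).
- Median, with d = 0.9 × 26 = 23.4 events and limits 2d × 14.6/χ²(2d): 10.1 to 22.9 months (printed 10 to 23).

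**2. Paths through two levels.** Levels 1 and -1, or Levels 1 and 2, take at most 6 + 6 = 12. The radiotherapy path reported so far (Level 1, then -1) is one of these.

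**3. Paths through three levels.** Every path above 12 starts with 0 of 3 at Level 1, finds Level 2 too toxic, finds at least 2 DLTs in the three patients added at Level 1, and then opens Level -1. In order (Level 1, Level 2, Level 1 again, Level -1):
- 3 + 3 + 3 + 6 = 15
- 3 + 6 + 3 + 3 = 15 (Level -1 also fails)
- 3 + 6 + 3 + 6 = 18

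**4. Study totals.** With 20 in expansion and escalation patients counted in both ladders: 15 + 20 = 35 and 18 + 20 = 38, before replacements. If 32 were held and Level -1 became the maintenance MTD, at most 32 − (6 + 3) = 23 or 32 − (6 + 6) = 20 patients would be treated at it, not 26.

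**5. How likely.** Let A be the chance of at least 2 DLTs in 3 at Level 1. Let S be the chance that Level 2 fails in its first three, and T the chance that it fails only after six (0 of 3 then at least 2 of 3, or 1 of 3 then at least 1 of 3). Let U be the chance of at least 2 in 3 at Level -1. After 0 of 3 at Level 1, P(more than 12) = A × [T + S(1 − U)]. From the start, multiply by (1 − p₁)³, where p₁ is the Level 1 rate. Six patients are taken as needed at Level 2 for it to be the MTD.

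| Assumed DLT rate at -1/1/2 | A | S | T | U | After 0 of 3 | From start |
|---|---|---|---|---|---|---|
| 5/10/15% | 0.028 | 0.061 | 0.163 | 0.007 | 0.6% | 0.5% |
| 5/10/20% | 0.028 | 0.104 | 0.241 | 0.007 | 1.0% | 0.7% |
| 5/15/30% | 0.061 | 0.216 | 0.364 | 0.007 | 3.5% | 2.2% |
| 10/20/35% | 0.104 | 0.282 | 0.399 | 0.028 | 7.0% | 3.6% |
| 10/25/40% | 0.156 | 0.352 | 0.415 | 0.028 | 11.8% | 5.0% |
| 10/30/50% | 0.216 | 0.500 | 0.391 | 0.028 | 18.9% | 6.5% |

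Last row: 0.216 × [0.391 + 0.500 × 0.972] = 0.189, and 0.189 × 0.70³ = 0.065.

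**6. The expansion count.** 20 + 3 = 23, and 12 + 23 = 35, not 32. Either 20 + 6 or 23 + 3 gives 26; neither pair is stated.

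**The case against.** - **Level -1 is for de-escalation only.** On this view the two escalation levels are Levels 1 and 2, and 2 × 6 is right. The arithmetic is right. What does not follow is the word maximum, since the ladders include Level -1 and the trial has used it.
- **The decision table never reaches 15 or 18.** Its backfill clause adds three patients at the next lower level only if three were treated there before. Read literally, an untreated Level -1 receives nobody and the path ends at 12. This stands as a limit: 15 and 18 rest on inferring that Level -1 is opened and filled to six under the MTD definition. Its use on the radiotherapy ladder makes the inference reasonable but does not make it text.
- **The 20+3 may be a tolerance.** With 23 in expansion, 3 at the MTD and 6 at another level, the sum is 32. That is possible but unstated, so the mismatch is loose wording and not proof that more than 32 were planned.
- **The toxicity rates may be lower.** Sections 4.2.1 and 5.3 cite earlier studies supporting the 400 mg maintenance dose with temozolomide, though without pembrolizumab. The two lowest scenarios allow for this, and the chance falls to 1% or less.

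A reader might also infer that two separate ladders need separate patients, and so a much larger total. The documents do not support that: Section 2.1 has one escalation cohort, Section 5.3 takes that cohort through both phases, and Section 1.0 lists one treatment group. Shared patients are the natural reading; only the written counting rule is missing.

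**Conclusion.** The point holds as a defect in the stated enrollment ceiling. Twelve and 32 are correct for two-level paths and are not true maxima once Level -1 can follow Level 2. On the inferred reading a ladder can reach 15 or 18, and the study 35 or 38 with shared escalation patients and 20 in expansion. Replacement of inevaluable patients (Section 5.9) and the instruction to add at least three patients (Section 5.3.1) mean that no figure here is a firm cap.

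The probability is small and rests wholly on assumed rates: about 0.5% to 6.5% per ladder from the start, and 0.6% to 19% after 0 of 3 at Level 1. Section 5.3 does not settle whether 0 of 3 has occurred on the maintenance ladder.

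The conflict between 20 and 20+3 is plain on the page and needs no assumption.

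Two stronger conclusions are not supported. The documents do not show that 12 or 32 has been exceeded; the reported radiotherapy path fits within 12. Nor are the survival intervals wrong; all three reproduce at n = 26. The practical effect is modest.

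**What to change.** In Sections 1.0 and 8.1:

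1. Restate the escalation maximum to include Level -1 (up to 18 evaluable with cohorts of three) and the study maximum that follows (38 if escalation patients count in both ladders). Alternatively, say that 12 and 32 hold only for paths through two levels. Either way, say that replacements are additional and, if it is so, that a patient counts in both ladders.
2. Replace 20+3 and 6+/-3 with one pair of counts that sums to 26 and agrees with Section 2.2.

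Keep the printed intervals; no others are needed. Sections 2.2, 5.3, 5.3.1 and 8.1 must be reconciled on whether and how Level -1 is opened after Level 2. No dose or escalation rule is proposed here.

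The cost is wording, plus approval and supply planning if a higher ceiling is stated. No patients are added unless such a path occurs.
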